8. INTERVENTION DISCONTINUATION

Safety findings that would prompt temporary suspension of enrollment and/or study interventions until a complete safety review is convened (either routine or ad hoc) include the following – lasting longer than 5 minutes:

- 1) Finger splay
- 2) Grimacing
- 3) Vital Sign disturbances associated directly with intervention
- 4) Crying

Should these findings last longer than 5 minutes in duration during intervention, the intervention will be stopped for that intervention session. If that preterm displays these findings >50% of their sessions within any one week (i.e., in 4, 5, or 6 sessions in that week), the intervention will be halted for 3 days and then re-initiated. During the 3 days of intervention halting for that infant, the NICU staff will be consulted on whether they recommend protocol modification for this preterm upon re-initiation. If this happens again (i.e., findings at 4, 5, or 6 sessions within one week) for this preterm after re-initiation, the intervention will be discontinued for that preterm but outcome measures will still be collected for that infant's complete follow-up.

After the first 3 preterms have been enrolled, if 2 or 3 of the 3 enrolled preterms have this temporary halting of the intervention, the DSMB/ CTSI Independent Monitor(s) will be consulted regarding whether the protocol should be modified. After at least 10 infants have been enrolled, if >40% of infants have this temporary halting of the intervention, the DSMB/ CTSI Independent Monitor(s) will be consulted regarding whether the protocol should continue as is, proceed with enhanced monitoring, be further investigated, be discontinued, or be modified and then proceed. Suspension of enrollment (for a particular group, a particular study site or for the entire

study) is a potential outcome of a DSMB/ CTSI Independent Monitor(s) safety review.

Subsequent review of serious, unexpected, and related AEs by the DSMB/ CTSI Independent Monitor(s), IRB, and NCCIH or relevant local regulatory authorities may also result in suspension of further study interventions/ administration of study product at a site. NCCIH retain the authority to suspend additional enrollment and study interventions/administration of study product for the entire study, as applicable.

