- 2) Added music exposure form to gather information on how much music is played at home after NICU discharge

Version Number 4.0

Version Date: August 31, 2020

Page 5, 15, 17, 18, 25: COVID efforts:

Given the need to decrease face to face interactions for COVID precautions, we are slightly decreasing the number of music intervention to an average of 4-5 (instead of 5-6) sessions per week. This is still

frequent enough music intervention to show changes in pain responses and neurodevelopmental findings since the intervention lasts a target of 6 weeks.

Page 5: ...average 4-5 intervention or control sessions per week...

Page 15: MBI subjects will receive ... intervention averaged at 4-5 sessions per week.

Page 17: ...music intervention 4-5 sessions per week...

Page 18: Adherence ...as 80% compliance ...average of 4-5 intervention or control sessions per week Page 25: Targeted averaged 4-5 sessions of MBI or Control will be played per week.

Page 16 and 18: Change 6 to 10 playlists:

To randomize songs properly, our biostatistician created 10 playlists, instead of the 6 originally planned. Page 16: stimulation, habituation, and neurological development, we will use ten playlists. Page 18: As it is recommended to change song order to increase stimulation, habituation, and neurological development, we will use 10 playlists.

Page 16: "decibel" to "volume":

The mp3 player/headphone equipment decibel levels will be checked prior to use. Because the mp3 players only display volume levels, this word was changed from "decibel" to "volume".

Page 16: Daily electronic volume level checks will avoid the need for listening checks of the headphones.

Version Number 5.0

Version Date: March 16, 2021

Pg 14: Clarification that for reliability in scoring, the PIPP will be

done by 2 study team members. The 2nd PIPP can be done in-person or virtually.

Pg 21 and 23 (sec 6.1 and 6.2.2 clarification that HADS is optional for the parent to complete)

Pg 24 (sec 6.2.4): clarification that EEG will have a video component

Pg 25: Hearing status of the child will be confirmed through chart review of the child's clinical BAER hearing test. This is done clinically prior to discharge (and/or at 1 month clinical care follow-up).

Pg 36 (sec 11.3) clarification the confidentiality of the video EEG

Version Number 6.0

Version Date: August 11, 2021

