5. STUDY INTERVENTIONS

5.1 Interventions, Administration, and Duration_

Specific recorded lullabies with simple arpeggiated accompaniment will be played for 6 weeks (+/- 1 week) in a small randomized, blinded, controlled study of 60 recruited medically stable 30 week preterms.

MBI subjects will receive a total of 1.5 hours of music intervention 4-5 sessions per week. Music will be alternating: 30 minutes on and 30 minutes off and will be played when the subject is awake to cue pacification and initiate the sleep process. Voice unaccompanied or with single accompanying

softly arpeggiated instrument is best for infants. Lullabies meet these criteria and promote language development due to an emphasis on vowels, rising and falling melodic phrases, and the recognition of soothing sounds. Lullabies will all have consistent tempos, with the melody in higher range sung by female or children as infants hear these pitches best. As it is recommended to change song order to increase stimulation, habituation, and neurological development, we will use 10 playlists. MP3 players will be loaded in advance with the entire 6 weeks of music. Within each week, order of the playlists will be randomly assigned and prepared in advance by [name]. MBI will have minimal interference with routine medical care.

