5.4 Adherence Assessment

Adherence is defined as 80% compliance in this study – average of 4-5 intervention or control sessions per week. If adherence falls below 80%, the Internal QA Reviewer will discuss with the PI methods for improving adherence.

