6.2.5 Music Based Intervention or Control Sessions

Targeted averaged 4-5 sessions of MBI or Control will be played per week. With each session of intervention, evaluations of vital signs and MBI information will be obtained. Target 6 weeks of MBI or control (+/- 1 week).

- Vital Signs
- MBI Information

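### Section 8's 3-day halt rule states two thresholds that disagree at the current 4-5 sessions per week: more than half means 3 or more sessions, but the count given for it starts at 4

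*Combined protocol and SAP*

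**What the plan says.** Section 8 (Intervention Discontinuation) sets a ladder of responses to finger splay, grimacing, vital sign disturbance or crying that lasts more than 5 minutes.

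- **Session:** the session is stopped.
- **Week:** if the infant shows "findings >50% of their sessions within any one week (i.e., in 4, 5, or 6 sessions in that week", then "the intervention will be halted for 3 days and then re-initiated", and NICU staff are consulted during the pause.
- **Repeat:** "If this happens again (i.e., findings at 4, 5, or 6 sessions within one week) for this preterm after re-initiation", the intervention is discontinued for that infant, with outcomes still collected.
- **Trial:** the DSMB/independent monitors are consulted if 2 or 3 of the first 3 infants have had the halt, and again, once at least 10 are enrolled, "if >40% of infants have this temporary halting of the intervention".

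The session frequency is set elsewhere. Section 5.1 says "MBI subjects will receive a total of 1.5 hours of music intervention 4-5 sessions per week", and Section 6.2.5 says "Targeted averaged 4-5 sessions of MBI or Control will be played per week". Section 5.4 adds "Adherence is defined as 80% compliance in this study", followed by the same 4-5 average.

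**The concern.** The halt sentence presents a percentage and a count as the same threshold. They are the same only for some weekly session numbers, and the numbers the plan now targets are not among them. The discontinuation step refers back to the halt rule, but its own parenthesis gives only the count, so the text does not show that the percentage takes precedence.

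What depends on the reading is a safety action in preterm infants: whether a distressed infant gets the 3-day pause and staff consultation, whether a repeat ends the intervention, and how many halts count toward the two DSMB/monitor triggers. Sections 7.2 and 9.4 are marked not applicable, so Section 8 holds the plan's only numeric halting rule. Two coordinators could apply it differently to the same infant, and a monitor could not say which of them had deviated.

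**Working it through.** **Inputs from the documents.** Threshold by percentage: more than 50% of the week's sessions. Threshold by count: at least 4 (Section 8). Sessions per week: an average of 4-5 (Sections 3, 5.1, 5.4, 6.2.5). Duration: a target of 6 weeks.

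**Step 1: does the count reproduce the percentage?** The smallest whole number of sessions exceeding half of n is floor(n/2) + 1.

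| Sessions in week (n) | Minimum for >50% | Minimum by count | Count minimum as share of n |
|---|---|---|---|
| 3 | 2 (67%) | 4 | cannot be met |
| 4 | 3 (75%) | 4 | 100% |
| 5 | 3 (60%) | 4 | 80% |
| 6 | 4 (67%) | 4 | 67% |

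The stated count is right for n = 6. For n = 4 and n = 5 the two forms conflict when exactly 3 sessions show findings. For n = 3 they conflict at 2 or 3.

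**Step 2: can 3-session weeks occur?** If Section 5.4 means 80% of the targeted sessions, an adherent infant averages 0.80 × 4 = 3.2 to 0.80 × 5 = 4.0 sessions per week, so such weeks fit the plan. The line could also mean that averaging 4-5 is itself the standard. Single weeks of 3 are still possible then, because 4-5 is an average.

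**Step 3: how far apart are the readings?** The documents give no per-session rate of findings over 5 minutes, so a rate p is assumed over a range, with independent sessions. With X ~ Binomial(n, p), the weekly halt probability is P(X ≥ floor(n/2) + 1) by percentage and P(X ≥ 4) by count. For example, with n = 4 and p = 0.3, the percentage gives 4 × 0.3³ × 0.7 + 0.3⁴ = 0.0756 + 0.0081 = 0.0837, and the count gives 0.3⁴ = 0.0081.

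Weekly halt probability, percentage vs count:

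| p | n = 3 | n = 4 | n = 5 | n = 6 |
|---|---|---|---|---|
| 0.1 | 2.8% vs 0 | 0.37% vs 0.01% | 0.86% vs 0.05% | 0.13% both |
| 0.3 | 21.6% vs 0 | 8.4% vs 0.8% | 16.3% vs 3.1% | 7.0% both |
| 0.5 | 50% vs 0 | 31% vs 6% | 50% vs 19% | 34% both |

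Probability of at least one halt over six such weeks, 1 − (1 − weekly)⁶, percentage vs count:

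| p | n = 4 | n = 5 |
|---|---|---|
| 0.1 | 2.2% vs 0.06% | 5.0% vs 0.3% |
| 0.3 | 41% vs 5% | 66% vs 17% |
| 0.5 | 89% vs 32% | 98% vs 71% |

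**Step 4: the 40% trigger.** At p = 0.3 the expected share of infants ever halted is above 40% by percentage (41% or 66%) and well below it by count (5% or 17%). At p = 0.2 with 5 sessions, the weekly values are 5.8% and 0.7%. Over six weeks that is 1 − (1 − 0.0579)⁶ = 30% against 1 − (1 − 0.0067)⁶ = 4%, so both fall below the trigger on average.

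**The case against.** The strongest reply is that little turns on this rule. The session is stopped after 5 minutes of findings on either reading, each stop goes to the PI, and the opening of Section 8 allows suspension for such findings without any weekly count. The study is classed as minimal risk, and the DSMB triggers lead to consultation, not to automatic stopping. All of that is true. It limits the harm, but none of it says when the 3-day halt or the discontinuation applies.

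Second, 6-session weeks are still possible: 4-5 is an average, and Section 6.1a has 36 session columns, which is 6 per week for 6 weeks. So the count is correct for the fullest week. It remains wrong for weeks of 4 or 5, the targeted numbers. The revision history for version 4.0 suggests how this arose: "we are slightly decreasing the number of music intervention to an average of 4-5 (instead of 5-6) sessions per week". The mismatch already existed for 5-session weeks under the older schedule; at the current target it affects 4-session weeks as well.

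Third, the probabilities rest on assumed rates and independence. Nothing in the documents supports 0.3 or 0.5, and distress probably clusters within infants. A few infants with findings in most sessions would meet both thresholds, which could narrow the gap. This stands: the figures illustrate the difference and are not forecasts. The contradiction in Step 1 needs no assumed rate.

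Fourth, a percentage is awkward if judged during the week, since one positive first session is 100%. That is a fair drafting point, and the corrected text should deal with it.

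**Conclusion.** The concern holds. The halt rule contradicts itself at the session frequency the plan now sets: with 4 or 5 sessions in a week, the percentage acts at 3 and the count at 4. With 3 sessions, the percentage acts at 2 and the count never acts. This follows from whole-number arithmetic alone.

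The practical size depends on an unknown distress rate. With independent sessions, the weekly gap is below 1 percentage point at a rate of 0.1 for 4 or 5 sessions, about 8 to 13 points at 0.3, and 25 to 31 points at 0.5. Efficacy power and the Go/NoGo thresholds do not change. It should be fixed because it is a decision threshold in a safety rule that feeds individual discontinuation and both DSMB/monitor triggers.

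**What to change.** Use one threshold at both places in Section 8, the halt and the repeat. Preferred: findings in more than half of the sessions delivered that week, meaning 2 or more of 3, 3 or more of 4 or 5, and 4 or more of 6. State how weeks with 1 or 2 sessions are handled, and that the proportion is judged on the completed week (or define the running rule intended).

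If the sponsor and DSMB intend the stricter rule, delete the percentage, keep the minimum of 4, and state openly that a week with 3 or fewer sessions cannot trigger a halt.

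Either version is a wording correction at two places, with no cost in data, staff or sample size.

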6.1 Schedule of Evaluations – Screening and Study Visits

**optional element (parent must provide specific consent to complete this assessment)*

** Family Feedback may be completed at any point before discharge from the hospital

6.1a Schedule of Evaluations – Music Based Intervention or Control Sessions

Assessment	1	2	3	4	5	6	7	8	9	10	11	12	13	14	15	16	17	18
Vital Signs	x	X	x	x	x	X	X	X	X	X	X	x	X	Х	Х	Х	Х	x
MBI Info Form	X	X	X	X	X	X	X	X	X	X	X	X	X	X	X	X	X	X
Assessment	19	20	21	22	23	24	25	26	27	28	29	30	31	32	33	34	35	36
Vital Signs	x	X	X	x	X	X	X	X	X	X	X	x	X	X	X	X	X	x
MBI Info Form	x	x	X	x	X	x	x	X	X	X	X	x	X	X	X	X	X	X

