6.2.3 Blinding

Blinding will be maintained by using identical headphones and MP3 players for all subjects. The PI, any personnel involved in collecting the clinical outcomes (e.g., PIPP) or collecting or quantifying EEG outcomes, and the statistician will be blinded. The statistician will be aware of blinded treatment group, so that e.g. safety summaries by blinded treatment group can be prepared for the Data Safety and Monitoring Board (DSMB) closed sessions if it so requests. Should the DSMB request unblinded comparisons, the study team will contract with the University of Minnesota CTSI's Biostatistical Design and Analysis Center (BDAC) for an independent statistician to work with the DSMB using unblinded data.

The unblinded staff includes [name] (music therapist) and [name] (Director of the NICU). [name] will prepare the music players. Both will be unblinded to handle randomization, delivery of interventions, and preparations of unblinded reports to the independent study monitors. They will not be involved with data monitoring, analyses, or outcome assessments.

The study coordinators who are assessing the PIPP will wear earplugs and noise cancelling headphones, which will ensure that s/he cannot hear what is emanating from the infant's headphones. In addition, family members and NICU staff will be reminded frequently to not disclose what they think they hear coming from the infant's headphones.

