Blinding will be maintained by using identical headphones and MP3 players for all subjects. The PI, any personnel involved in collecting the clinical outcomes (e.g., PIPP) or collecting or quantifying EEG outcomes, and the statistician will be blinded. The statistician will be aware of blinded treatment group, so that e.g. safety summaries by blinded treatment group can be prepared for the Data Safety and Monitoring Board (DSMB) closed sessions if it so requests. Should the DSMB request unblinded comparisons, the study team will contract with the University of Minnesota CTSI's Biostatistical Design and Analysis Center (BDAC) for an independent statistician to work with the DSMB using unblinded data.

The unblinded staff includes [name] (music therapist) and [name] (Director of the NICU). [name] will prepare the music players. Both will be unblinded to handle randomization, delivery of interventions, and preparations of unblinded reports to the independent study monitors. They will not be involved with data monitoring, analyses, or outcome assessments.

The study coordinators who are assessing the PIPP will wear earplugs and noise cancelling headphones, which will ensure that s/he cannot hear what is emanating from the infant's headphones. In addition, family members and NICU staff will be reminded frequently to not disclose what they think they hear coming from the infant's headphones.

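### Section 8 defines the temporary halt by a percentage and a session count that disagree at the planned 4-5 sessions per week, so the halt and both study-level triggers built on it have two readings

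*Combined protocol and SAP*

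**What the plan says.** Section 8 builds its safety rules in layers.

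- **Session:** distress findings lasting longer than 5 minutes stop that session.
- **Infant:** findings in ">50% of their sessions within any one week (i.e., in 4, 5, or 6 sessions in that week") lead to a 3-day halt. If this recurs after restarting, the intervention is discontinued for that infant. The restatement for discontinuation gives only the count of 4, 5 or 6 sessions.
- **Study, early:** after the first three enrolments, the DSMB or independent monitors are consulted "if 2 or 3 of the 3 enrolled preterms have this temporary halting of the intervention".
- **Study, later:** they are consulted again on this condition: "After at least 10 infants have been enrolled, if >40% of infants have this temporary halting of the intervention".

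On the number of sessions, Section 6.2.5 states: "Targeted averaged 4-5 sessions of MBI or Control will be played per week". Sections 3 and 5.1 give the same 4-5 per week, for a target of 6 weeks plus or minus 1. The table headed "6.1a Schedule of Evaluations" for intervention or control sessions has columns for 36 sessions. The revision history for version 4.0 records the reduction from 5-6 to 4-5 sessions per week and lists the pages changed. The entries it describes are the session frequency and the adherence definition; the halting rule is not among them.

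**The concern.** Section 8 presents the percentage and the count as the same rule, but at the planned frequency they are different rules. An infant distressed in 3 of 4 or 3 of 5 sessions in a week meets the percentage and misses the count. Two members of staff applying the same sentence could reach opposite conclusions about that infant.

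The ambiguity carries upwards. Discontinuation depends on a second halt, and both consultation triggers count halted infants. Until the two thresholds agree, neither the early rule nor the 40% rule has a defined numerator.

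**Working it through.** **1. Does the count reproduce the percentage?** Let n be the sessions held in a week. More than 50% means more than n/2 sessions.

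| Sessions in week (n) | n/2 | Fewest sessions exceeding 50% | What 4 sessions represents |
|---|---|---|---|
| 4 | 2 | 3 (75%) | 100% |
| 5 | 2.5 | 3 (60%) | 80% |
| 6 | 3 | 4 (67%) | 67% |

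The count of 4, 5 or 6 reproduces the percentage at n = 6. It does not at n = 4 or n = 5, which is the planned average.

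**2. Session table.** 36 sessions / 6 weeks = 6 per week. The current plan gives 4 x 6 = 24 to 5 x 6 = 30 sessions in 6 weeks, and at most 5 x 7 = 35 with the extra week allowed. The table therefore matches a 6-session week, as the count in Section 8 does.

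**3. How much the reading matters.** The documents give no distress rate, so the chance p of a qualifying finding in a session is an assumption. Sessions are taken as independent, with a constant n per week for 6 weeks.

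- Weekly probability: a = P(X ≥ 3) under the percentage, b = P(X ≥ 4) under the count, with X binomial (n, p).
- Ever halted in 6 weeks: 1 − (1 − a)^6 or 1 − (1 − b)^6.

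Example, p = 0.2 and n = 4: a = 4(0.2³)(0.8) + 0.2⁴ = 0.0272 and b = 0.2⁴ = 0.0016. Over 6 weeks, 1 − 0.9728^6 = 0.152 and 1 − 0.9984^6 = 0.010.

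| p | n | Weekly, percentage | Weekly, count | Ever halted, percentage | Ever halted, count |
|---|---|---|---|---|---|
| 0.1 | 4 | 0.0037 | 0.0001 | 2.2% | 0.1% |
| 0.1 | 5 | 0.0086 | 0.0005 | 5.0% | 0.3% |
| 0.2 | 4 | 0.0272 | 0.0016 | 15% | 1% |
| 0.2 | 5 | 0.0579 | 0.0067 | 30% | 4% |
| 0.3 | 4 | 0.0837 | 0.0081 | 41% | 5% |
| 0.3 | 5 | 0.1631 | 0.0308 | 66% | 17% |

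**4. Effect on the early trigger.** If q is the chance that an infant is ever halted, the same for each of the first three, then P(2 or 3 of 3) = 3q²(1 − q) + q³. With p = 0.2 and n = 5, q = 0.301 gives about 22% and q = 0.040 gives about 0.5%. With n = 4 the figures are about 6% and 0.03%.

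**5. Secondary matter: pooling of arms.** Neither trigger names an arm. Allocation is 50:50 (Section 4.3) and controls hear silence (Section 3). At an exactly balanced look with observed halting rates m on music and c on silence, the pooled rate is (m + c)/2, so exceeding 40% means m + c > 80%. At 60 infants with none halted on silence, 25 of 30 on music gives 25/60 = 41.7% and meets the condition; 24/60 is exactly 40% and does not. This is a statement about observed rates. In simulation with sex-stratified blocks of 2 and 4 and a check after every enrolment from 10 to 60, assumed true rates of 50% and 10% (sum 60%) met the condition at some point in about 37-38% of trials, and 50% and 20% (sum 70%) in about 62%.

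**The case against.** **On the halt definition.** The 4-5 sessions are an average, so a 6-session week can occur, and there the two thresholds agree. The discontinuation sentence uses the count alone, so one could treat the count as operative. Neither removes the problem: the sentence that first defines the halt gives both thresholds as equivalent, and weeks of 4 or 5 sessions are what the plan targets. Nor should the revision history be over-read. It is consistent with Section 8 having been left behind when sessions were cut, but it does not prove this, and the count would already have failed in a 5-session week under the previous 5-6. The inconsistency rests on the current text alone.

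**On pooling.** A reader might infer that the pooled triggers leave an excess of distress on music unseen, or that the 40% rule cannot fire unless true halting rates sum above 80%. The documents do not support either inference.

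- The session stop, 3-day halt and discontinuation act on each infant whatever the arm.
- The triggers lead only to consultation, and Section 8 opens with a list that has no pooled percentage: "Safety findings that would prompt temporary suspension of enrollment and/or study interventions until a complete safety review is convened".
- Sections 6.2.3 and 9.2 assign unblinded staff "preparations of unblinded reports to the independent study monitors", with no condition of request. Their content and timing are not stated, so it is not shown that they omit halts by arm.
- The DSMB may also ask for coded or unblinded comparisons.
- The 80% sum holds for observed rates at a balanced look. Chance, temporary imbalance and repeated checks can fire the rule at lower true rates, and the sum does not apply to the first-three rule, since three infants cannot be split equally.

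A pooled count is a legitimate monitor for a blinded team. What remains is a reporting preference: coded-arm summaries are described as "safety summaries by blinded treatment group can be prepared for the Data Safety and Monitoring Board (DSMB) closed sessions if it so requests".

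**Conclusion.** The contradiction in Section 8 is real and needs no assumed rate to establish: more than half of 4 or 5 sessions is 3, and the stated count starts at 4. Its consequence is potentially large. At an assumed 20% chance of distress per session, the chance that an infant is ever halted differs about 15-fold at 4 sessions per week (15% against 1%) and about 8-fold at 5 (30% against 4%). These sizes rest on independent sessions, a constant weekly number and the assumed rate. Distress that clusters within infants or weeks would change them, but 3 sessions would still qualify under one threshold and not the other.

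Pooling of the arms is not an error. It supports only an optional improvement in reporting, of low priority in a study described as minimal risk.

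**What to change.** **Main change.** In Section 8, reconcile the percentage and the session count at both places where the count appears (the 3-day halt and the discontinuation after restart) with the 4-5 sessions per week in Sections 3, 5.1 and 6.2.5, and with the 36-session table in 6.1a. State how the rule is read in weeks with different numbers of sessions. Which reading applies is for the sponsor and the DSMB to decide. The cost is a wording amendment. If infants have already been assessed under one reading, record which one was used so that the halt counts can be interpreted.

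**Optional.** Consider listing temporary-halt counts by coded arm routinely in the closed DSMB report instead of only on request, and state the content and timing of the unblinded reports to the monitors. Keep the pooled triggers and add no arm-specific threshold. This is a short table, but it has two costs. A lopsided split could hint at which code is music, so circulation should be limited to the independent reviewers. The preparer must also be settled: 6.2.3 keeps the unblinded staff out of data monitoring and analyses, and provides for the independent statistician only if the DSMB requests unblinded comparisons. Early counts by arm will be noisy and should be presented as information only.
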